8.2.2 Continuous Endpoints

For continuous endpoints, missing data will be handled using Mixed-Effect Model Repeat Measurement (MMRM).

- The MMRM will be conducted using mixed model including observed measurements at all visits, except that measurements after any rescue medication will be excluded. The mixed model includes the fixed effects of categorical variable of treatment, visit and treatment-by-visit interaction, main stratification factor at randomization (baseline vIGA-AD categories), and the continuous variable of Baseline measurement. An unstructured variance covariance matrix (UN) will be used. If the model cannot converge, an appropriate covariance structure matrix (e.g., autoregressive (1) or compound symmetry) will be used. The parameter estimations are based on the method of restrictive maximum likelihood (REML). The fixed effects will be used to report model-based means at corresponding visits.

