### 3.3 Secondary Endpoints

---

Ranked Secondary Endpoints:

1. Percent change from Baseline to Week 16 in Worst Pruritus Numerical rating scale (NRS)
2. Proportion of subjects achieving a 100% reduction in EASI (EASI 100) from Baseline at Week 16
3. Proportion of subjects achieving a 90% reduction in EASI (EASI 90) from Baseline at Week 16
4. Percent change from Baseline to Week 4 in Worst Pruritus NRS
5. Proportion of subjects achieving a 75% reduction in EASI (EASI 75) from Baseline at Week 2
6. Percent change from Baseline to Week 1 in Worst Pruritus NRS
7. Proportion of subjects achieving an improvement (reduction) in Worst Pruritus NRS  $\geq 4$  from Baseline at Week 16 for subjects with Worst Pruritus NRS  $\geq 4$  at Baseline

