8.1.1 Analysis of Efficacy Endpoints by Variable Type

Analysis of Categorical Variables

For ITT Population, frequencies and percentages will be summarized along with 95% confidence interval (CI) based on normal approximation. For ITT Population, pairwise comparisons of upadacitinib vs. dupilumab will be made using CMH test using stratification factor as baseline vIGA-AD categories (vIGA-AD 3 or 4). Point estimates, *p*-value, and 95% CIs for the difference in proportions between upadacitinib and dupilumab will be provided. Construction of CIs for the common risk difference will be based on the Mantel-Haenszel estimate adjusting for stratification factors. Breslow-Day test will be performed to test the homogeneity between strata.

NRI-C will be the primary approach for categorical endpoints (Section 8.2). In addition, the primary endpoint and all key secondary categorical endpoints will be analyzed using MI defined in Section 8.2 as the sensitivity approach. All categorical endpoints will be analyzed using NRI-NC defined in Section 8.2 as the sensitivity approach.

Analysis of Continuous Variables

For ITT Population, the Baseline and visit means will be presented for each treatment group who have both Baseline and post-baseline visit values. For ITT Population, Percent change from Baseline in the treatment groups will be compared using MMRM model as described in Table 1. Point estimates, SE, and 95% CIs of LS mean change from Baseline within treatment groups, and these statistics along with *p*-value between upadacitinib group and dupilumab will be provided.

Table 1. Model of Continuous Variables

Population	Model	Adjust for Stratification Factor(s)
ITT	MMRM model includes the categorical fixed effects of treatment, visit and treatment-by-visit interaction, and the continuous fixed covariates of Baseline measurement.	vIGA-AD categories at randomization

All efficacy endpoints will be analyzed overall and within each stratum of the stratification factors: baseline vIGA-AD categories and age group Analysis model within each stratum will not be adjusted for stratification factors.

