8.4.2 Supportive Secondary Efficacy Analyses

The NRI-C will be the primary approach for missing data handling in the analyses of the binary secondary efficacy endpoints. The NRI-NC approach will be used as sensitivity analyses. MMRM will be the primary and the only approach for continuous endpoint.

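### The MMRM uses one Baseline slope for all visits; adding Baseline-by-visit would protect a little precision in the Week 16 pruritus comparison at almost no cost

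*SAP*

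**What the plan says.** SAP 8.2.2 states: "The mixed model includes the fixed effects of categorical variable of treatment, visit and treatment-by-visit interaction". To these it adds the "main stratification factor at randomization (baseline vIGA-AD categories), and the continuous variable of Baseline measurement". Table 1 in SAP 8.1.1 gives the same model: "MMRM model includes the categorical fixed effects of treatment, visit and treatment-by-visit interaction, and the continuous fixed covariates of Baseline measurement", adjusted for vIGA-AD category. Neither place lets the Baseline effect differ by visit.

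The model is fitted "including observed measurements at all visits, except that measurements after any rescue medication will be excluded". On covariance: "An unstructured variance covariance matrix (UN) will be used", with AR(1) or compound symmetry as examples of a fallback if the fit does not converge. SAP 8.4.2 says "MMRM will be the primary and the only approach for continuous endpoint". SAP 8.1.1 also plans analyses within each vIGA-AD and age stratum, but nothing there lets the Baseline slope vary by visit.

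Protocol 3.3 ranks percent change in Worst Pruritus NRS first (Week 16), fourth (Week 4) and sixth (Week 1). SAP 11.0 tests in fixed sequence after the primary endpoint, so failure at Week 16 stops the other six. Protocol 5.4 leaves rescue to the investigator's discretion. Neither document gives a rescue rate by arm, a link between rescue and Baseline pruritus, or an SD, correlation or Baseline slope by visit.

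**The concern.** A common slope says that one extra Baseline NRS point shifts percent change by the same number of percentage points at every visit. Percent change divides by Baseline, and its mean and spread usually grow as treatment takes effect, so equal slopes would need a special relation between score and Baseline at each visit. The measure also changes within the treatment period: weekly rolling averages up to Week 16, then single clinic scores (SAP 8.1.2 and Appendix I).

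The SAP does not impose this restriction elsewhere. The sequential regressions in Appendix F give each visit its own Baseline coefficient.

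If the slope does vary, Week 16 is adjusted with a slope that is not its own. At stake are some precision in the endpoint that gates the ranked secondaries and, under further conditions, a small shift in its estimate.

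**Working it through.** **1. The plan's own figure.** The only power statement is for EASI 75 (SAP 2.4): 50% vs 62%, 325 per arm, two-sided 0.05. With mean proportion 0.56, the null SE is √(2 × 0.56 × 0.44/325) = 0.0389 and the alternative SE is √((0.50 × 0.50 + 0.62 × 0.38)/325) = 0.0387. Power = Φ((0.12 − 1.96 × 0.0389)/0.0387) = Φ(1.13) = 87.1%. The stated figure of more than 80% is met. No power is given for pruritus, so every input below other than sample size and visit schedule is an assumption.

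**2. Which visits set the common slope.** With free visit means and covariance Σ, the common slope is a weighted average of the visit slopes, with weights proportional to the row sums of Σ⁻¹. For two visits with SDs 20 and 40 and correlation 0.5 (illustrative), the early weight is proportional to 1/400 − 0.5/800 = 0.001875 and the late weight to 1/1600 − 0.5/800 = 0. The late visit gets no say. With equal SDs each visit gets half.

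For eight visits (Weeks 1, 2, 4, 8, 12, 16, 20, 24):

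| Residual SD over time | Weight on Weeks 1–4, AR-type correlation | Weight on Weeks 1–4, compound symmetry |
|---|---|---|
| 20 rising to 40 | 82–90% | over 100% |
| 25 rising to 35 | 68–74% | 89–130% |

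With equal SDs, Weeks 1–4 carry only 37–52%. Early dominance therefore depends on early variance being lower.

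**3. Precision at Week 16.** Variance inflation = 1 + (slope gap × SD of Baseline)²/residual variance, where the gap is the Week 16 slope minus the common slope, in percentage points per NRS point. Baseline SD is taken as 1.3 to 1.6 (entry requires a weekly average of at least 4 on a 0–10 scale) and residual SD as 35 to 40. For a gap of 5, the low end is (5 × 1.3)²/40² = 42.25/1600 = 2.6% and the high end is (5 × 1.6)²/35² = 64/1225 = 5.2%. Power starting from 80% is Φ(2.80/√inflation − 1.96).

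| Gap | Variance inflation | Power |
|---|---|---|
| 1 | 0.1–0.2% | about 79.9% |
| 2 | 0.4–0.8% | 79.7–79.8% |
| 3 | 1.0–1.9% | 79.3–79.6% |
| 5 | 2.6–5.2% | 78.0–79.0% |
| 8 | 6.8–13.4% | 74.9–77.4% |

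**4. Simulation, no rescue.** Setting: 325 per arm, 1000 replicates, unstructured covariance, true difference 9 points.

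| Slope, early to Week 16 | Power, common slope | Power, Baseline-by-visit |
|---|---|---|
| 0 to −3 | 79.9% | 80.8% |
| −1 to −6 | 79.6% | 80.8% |
| 0 to −8 | 78.3% | 80.8% |

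Type I error with the common slope was 4.6–4.8%. The model SE tracked the empirical SE (3.24 vs 3.18 in the last row), because the unstructured covariance absorbs the slope misfit.

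**5. Bias.** Common-slope minus Baseline-by-visit estimate at Week 16, with an SE of the treatment effect of about 3.2:

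- Rescue depends on Baseline equally in both arms: 0.01 to 0.03, within simulation error. Type I error was 5.9–6.0% vs 5.8% (simulation SE about 0.7 points).
- Moderately different rescue by arm (about 10% vs 3% by Week 16): −0.07 to −0.18.
- Rescue tied strongly to Baseline in the dupilumab arm only (21% vs 7%): −0.43, −0.70 and −1.08 for the three slope patterns, at most about a third of an SE. Type I error was 5.6–6.3% vs 5.0%.

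A negative value favours upadacitinib. It arises here because higher Baseline goes with larger percent improvement and dupilumab has more rescue. A positive slope reverses it.

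**6. What slope change is plausible.** Scores generated with Baseline truncated to 4–10 (SD 1.35), mean NRS falling from 6 to 3 and residual SD rising from 1.2 to 2.2 gave Week 1 to Week 16 slope changes of 1.5 to 6.3, with a change of sign. A separate setting, with NRS clipped to its scale and residual SD of percent change rising from about 20 to 34, gave a Week 16 SE loss of only 0.01% to 0.5%, at most 1.005² − 1 = 1.0% of variance.

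**The case against.** The plan is clear, consistent between its two statements of the model, and executable. An additive Baseline covariate is a legitimate choice in a randomised trial. Unequal slopes and lower early variance are assumptions; with equal slopes nothing is lost. The gate is hardly threatened. With a true effect of 10 points, SD 33 and 325 per arm, the SE is 33 × √(2/325) = 2.59 and power is 97.1%. Inflating the SE by 1%, 5% or 10% leaves 96.9%, 95.7% or 94.0%. All of this stands, and it limits the point to a minor improvement.

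A reader might go further in three ways that the documents do not support.

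- That the model is biased whenever rescue depends on Baseline. Equal dependence in both arms gave about zero. Bias needs visit-varying slopes and selection on Baseline that differs by arm, and the documents establish neither. Harsher assumed missingness (16% to 21% at Week 16, depending on Baseline and arm) gave 1.3 to 2.5 points towards zero in 60 trials per scenario, the opposite direction to step 5. Size and sign follow the inputs.
- That the loss is like discarding 13% to 17% of subjects. That is a 7% to 10% larger SE (1 − 1/1.07² = 13%; 1 − 1/1.10² = 17%). It needs the Baseline–outcome correlation to swing from −0.3 to +0.3. With SDs of 18 and 33, the slope change is 0.3 × (18 + 33)/1.6 = 9.6 to 0.3 × (18 + 33)/1.3 = 11.8 points per NRS point.
- That vIGA-AD-by-visit is equally needed. No calculation supports it; every figure here concerns Baseline NRS.

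**Conclusion.** The specification point holds: the model for ranked secondaries 1, 4 and 6 has a single Baseline slope, and no other missing-data approach is planned for them. The consequence is small. For slope gaps up to about 5 points per NRS point, the Week 16 variance rises by 0% to 5%, costing 0 to 2 points of power near 80%. Only a gap near 8 costs about 3 to 5 points. Bias is conditional, of either sign, and about 0.1 to 0.2 points in the moderate case and about 1 point in the extreme one. These sizes rest on assumed SDs, slopes, correlations and rescue rates.

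The reassurance about validity is for the unstructured covariance. The AR(1) or compound-symmetry fallback lacks that flexibility and was not tested. None of this supports a claim that the ranked hierarchy is undermined. Severity is minor.

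**What to change.** In SAP 8.2.2 and Table 1, add the Baseline-by-visit interaction to the fixed effects, and estimate the LS mean differences at Weeks 1, 4 and 16 from that model. Make the change before the Week 24 database lock. Protocol Appendix D has 13 post-baseline visits with NRS, so the interaction adds 13 − 1 = 12 parameters for about 650 subjects; if slopes turn out equal, essentially nothing is lost. If the sponsor prefers to keep the present model as primary, the interaction model should at least be prespecified as a sensitivity analysis. A vIGA-AD-by-visit term, another 12 parameters, is optional.

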2.3 Treatment Assignment and Blinding

Subjects will be randomized to upadacitinib or dupilumab in a 1:1 ratio. Randomization will be stratified by baseline disease severity (moderate [vIGA-AD 3] vs. severe [vIGA-AD 4]), and age (< 40, \geq 40 - < 65, \geq 65).

The AbbVie study team, study site personnel, and subjects will be blinded to treatment assignment until the primary analysis. Thereafter, all study site personnel involved in the study and subjects will remain blinded to the subject's treatment throughout the study. The exception to this is the designated unblinded site staff responsible for administration of the injectable study drug who are unblinded for the entirety of the study.

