2.4 Sample Size Determination

Approximately 650 subjects (18 - 75 years old) will be randomized to upadacitinib 30 mg or dupilumab in a ratio of 1:1 (325 subjects per treatment group). Assuming an EASI 75 response rate of at most 50% in the dupilumab arm, this sample size will provide more than 80% power to detect at least a 12% treatment difference using two-sided test at a 0.05 significant level. The assumption of dupilumab response rate for EASI 75 at Week 16 and 12% treatment difference were based on the pooled response rates of dupilumab Phase 3 monotherapy studies (SOLO 1 and SOLO 2) and the response rate of upadacitinib 30 mg in the upadacitinib AD Phase 2b study.

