8.0 Efficacy Analyses

8.1 General Considerations

The Primary Analysis will be performed after all ongoing subjects have completed the Week 24 visit and the database has been locked. This will be the only and final analysis for the primary and key secondary efficacy endpoints as well as all other efficacy endpoints. All efficacy analyses will be conducted in the ITT Population. In addition, Per-protocol analysis for primary endpoint will be performed. All tests will be 2-sided at an alpha level of 0.05.

Categorical variables and continuous variables will be analyzed using Cochran-Mantel-Haenszel (CMH) and Mixed-Effect Model Repeat Measurement (MMRM) method, respectively.

"Baseline" refers to the last non-missing observation before the first administration of study drug or randomization if no study drug is given. When analyzing rolling-average-based endpoints, Baseline refers to the last available rolling average before the date of first administration of study drug.

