8.1.2 Analysis of Daily Efficacy Measurements

For daily efficacy assessments including the Worst Pruritus NRS, a rolling weekly average is calculated by using handheld device only to represent the corresponding endpoints by week on and before Week 16.

The weekly average of the daily values from a maximum of seven days immediately prior to the first dose date will be used as the Baseline value. The rolling weekly average score is calculated for each Day m , starting from Day 8 through the Week 16 visit or Study Day 120 as follows. Let $P_{m-6}, P_{m-5}, \dots, P_{m-1}, P_m$ be the daily score from Day $m-6$ to Day m , and N_m be the number of days with non-missing scores from Day $m-6$ to Day m , then the rolling weekly average for Day m is:

$$\frac{\sum_{i=m-6}^m P_i}{N_m}$$

If the values from four or more days of the seven-day period are missing, then the rolling weekly average of Day m will be set to missing. If more than one assessment is included on the same day, the assessment associated with the worst condition on that day will be

chosen as the daily score. Analysis value for a given visit will be selected from rolling averages based on analysis window conventions.

For the visits where the questionnaire is completed at the site, scores from single clinic visits will be used as the analysis value. However, these analysis values will not be included in rolling weekly average calculations.

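### The MMRM fallback covariance is left open, its only named examples assume equal variance at every visit, and no order, heterogeneous version or robust standard error is set

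*SAP*

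**What the plan says.** For continuous endpoints SAP 8.2.2 states: "An unstructured variance covariance matrix (UN) will be used". The fallback follows directly: "If the model cannot converge, an appropriate covariance structure matrix (e.g., autoregressive (1) or compound symmetry) will be used". The section specifies REML and a model over all visits, with values after rescue excluded. It gives no order of structures and no selection rule, and it names no standard-error estimator.

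The model serves three of the seven ranked secondary endpoints: percent change in Worst Pruritus NRS at Week 16 (rank 1), Week 4 (rank 4) and Week 1 (rank 6). SAP 8.4.2 makes MMRM the sole approach for continuous endpoints. SAP 11.0 tests the ranked endpoints in a fixed sequence, so a failure at one rank stops the ranks below it. SAP 8.1 sets the level: "All tests will be 2-sided at an alpha level of 0.05".

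The analysis value changes in kind over time. SAP 8.1.2 uses a rolling 7-day average of handheld scores up to Week 16. For visits where the scale is completed at the site, "scores from single clinic visits will be used as the analysis value". SAP Appendix I confirms that no rolling average is formed after Week 16.

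**The concern.** AR(1) and compound symmetry in their standard forms differ in correlation pattern but share one feature: a single residual variance for every visit. A visit-specific contrast from such a model takes its standard error from a variance pooled over all visits. If the true variance at Week 1, 4 or 16 differs from the pooled value, the standard error for that test is wrong, and more subjects do not cure it.

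The design gives some reason to expect unequal variances, because a single-day score varies more than a 7-day mean and both enter one model.

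The Week 16 test matters most. It is the first secondary endpoint, so too small a standard error there would open the rest of the hierarchy too easily, and too large a one could close it. With MMRM as the only continuous analysis, no second result would show the problem. The structure would also be chosen after the planned model had failed, with no rule to fix the choice.

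**Working it through.** **The plan's own power figure.** The only power statement concerns EASI 75: "325 subjects per treatment group", a dupilumab rate of at most 50%, and a 12-point difference at two-sided 0.05. With pooled rate 0.56, the null SE is √(2 × 0.56 × 0.44 / 325) = 0.03894. The alternative SE is √((0.50 × 0.50 + 0.62 × 0.38) / 325) = 0.03865. Power = Φ((0.12 − 1.96 × 0.03894) / 0.03865) = Φ(1.13) = 87.1%, so the claim of more than 80% is correct. It does not bear on the NRS tests, for which no power or SD is stated.

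**Number of covariance parameters.** Protocol Appendix D marks Worst Pruritus NRS at 13 on-treatment visits (Weeks 1, 2, 4, then every 2 weeks to 24). If all are used, the unstructured matrix has 13 × 14 / 2 = 91 parameters, for about 650 subjects. The nine visits to Week 16 would need 9 × 10 / 2 = 45.

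**Standard error under a common-variance structure.** With complete data the visit contrast is the difference in means. The compound-symmetry fit converges to the average of the visit variances, so

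- SE ratio at a visit = √(mean of the 13 visit variances) / SD at that visit;
- true two-sided error = 2Φ(−1.96 × SE ratio).

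Both use model-based standard errors, which is an assumption because the SAP names no estimator.

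**Assumed SD profile.** Set the Week 1 SD to 1 and the Week 16 SD to r, with equal steps over the nine visits between, and SD = r at the four later visits. For r = 2 the first nine squared SDs sum to 21.19 and the last four to 16. The pooled SD is √(37.19 / 13) = 1.69. The SE ratios are 1.69 / 1 = 1.69 at Week 1, 1.69 / 1.25 = 1.35 at Week 4 and 1.69 / 2 = 0.85 at Week 16. The same steps for other values of r give SE ratio (error):

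| r | Week 1 | Week 4 | Week 16 |
|---|---|---|---|
| 0.8 | 0.87 (8.7%) | 0.92 (7.2%) | 1.09 (3.3%) |
| 1.0 | 1.00 (5.0%) | 1.00 (5.0%) | 1.00 (5.0%) |
| 1.25 | 1.17 (2.2%) | 1.10 (3.1%) | 0.93 (6.7%) |
| 1.5 | 1.34 (0.9%) | 1.19 (2.0%) | 0.89 (8.0%) |
| 2.0 | 1.69 (0.1%) | 1.35 (0.8%) | 0.85 (9.7%) |

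Best-fitting AR(1) ratios lie within about 0.03 of these.

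**Effect of the switch to single scores.** If days within a week correlate at ρ, the single-day SD exceeds the 7-day-mean SD by a factor √(7 / (1 + 6ρ)): 1.23 at ρ = 0.6 and 1.05 at ρ = 0.9 (assumed range). Take 15% after Week 16:

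- r = 1.0: pooled SD = √((9 + 4 × 1.3225) / 13) = 1.05, so the SE is about 5% too large at all three weeks (error about 4%).
- r = 1.25: the Week 16 ratio is 0.99 (5.3%), with 1.23 at Week 1 and 1.16 at Week 4.
- r = 1.5: the Week 16 ratio is 0.95 (6.4%).

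Larger later SDs therefore offset a too-small SE at Week 16 and add to a too-large one at Weeks 1 and 4.

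**Simulation check.** This used 1,500 trials of 650 subjects per setting, with a compound-symmetry working model, r = 1.5, equal later SDs, and treatment-by-visit means without the baseline and vIGA-AD covariates. The Monte Carlo SE is about 0.6 points. Error at Weeks 1 / 4 / 16:

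| | Model-based SE | Sandwich SE |
|---|---|---|
| Complete data | 1.1 / 2.1 / 8.3% | 5.9 / 5.4 / 5.4% |
| About 20% dropout | 1.1 / 1.9 / 7.5% | 5.7 / 4.9 / 4.2% |

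With equal variances, complete data and a wrong correlation pattern, the simulated error was 4.7% to 5.0%. The unequal variance does the harm.

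**The case against.** The strongest reply is that the planned model already handles this. An unstructured matrix has a separate variance for each visit and absorbs the change from averages to single scores. The fallback acts only on non-convergence, and 91 parameters with about 650 subjects make that possible but not expected. This stands for the ranked tests. Failure is more plausible in the within-stratum analyses of SAP 8.1.1: SAP 8.6 allows that the group aged 65 and over may hold fewer than 10% of subjects, that is, fewer than 65 of 650. Those analyses are not ranked.

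Second, a reader might infer that the SAP imposes equal variances. It does not. The two structures are examples of an appropriate one, and a heterogeneous version is not excluded. The gap is an open choice whose only examples point the wrong way.

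Third, a reader might infer that the fallback inflates the Week 16 test and costs power at Week 1. That needs spread to grow from Week 1 to Week 16, and neither document gives an SD by visit. If spread shrinks (r = 0.8), the pattern reverses.

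Finally, the trigger is numerical non-convergence and not the treatment estimate, so the concern about a late choice is limited to the missing order.

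**Conclusion.** The point holds as a conditional weakness that is cheap to remove. It needs three things together: the unstructured model fails, an equal-variance structure with model-based standard errors replaces it, and residual variance differs by visit. The third is plausible because of the change in measurement after Week 16; the first is not the expected case.

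Given all three, the error rate at Week 16 lies between 3.3% and 9.7% over the assumed SD ratios with equal later SDs. It can be near nominal when later SDs are larger. Neither a direction nor a single figure for this trial can be drawn from the documents. The CMH analysis of the primary endpoint and the ranked responder endpoints does not use this model. The ranked responder endpoints can still be affected through the testing sequence.

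**What to change.** In SAP 8.2.2, replace the examples with an ordered list: heterogeneous Toeplitz, then heterogeneous AR(1), then heterogeneous compound symmetry, using the first that converges. State that any fit that is not unstructured uses empirical (sandwich) standard errors. The simulation tested the sandwich part on a compound-symmetry fit, where it brought the Week 16 error from 8.3% to 5.4% with complete data. The heterogeneous sequence itself was not simulated; its case is that it keeps visit-specific variances.

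Optionally, restrict the models for the ranked tests to visits up to Week 16. That cuts the unstructured matrix from 91 to 45 parameters and keeps single clinic scores out, but it is not needed when the unstructured model converges.

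The cost is one SAP sentence, written before unblinding, with no change to data collection or sample size.
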